6.3.5 On Study Visits

Clinical/Nonclinical staff Consent/Baseline Visit: A trained RA will send an email with RedCap link containing consent to all clinical/nonclinical staff via a general email distribution list. After clicking on the link, potential participants will read the 'consent statement' which includes PI name, brief study purpose, details on voluntary participation, ability to stop at any time without explanation and further, that such action will in no way affect their relationship with the primary care practice, confidentiality (anonymous survey), risks/benefits, etc. The email will emphasize that participation is voluntary and refusal to participate will not affect employment or job performance evaluation. They will then be given the option of whether they choose to participate. If they choose to participate, they will proceed to the survey, otherwise, participants will terminate the survey. Following informed consent, clinical/nonclinical staff will complete baseline measures of demographics, implementation climate, organizational capacity to change, individual attitudes toward evidence-based practices, and provider trust. These measures should take 20 minutes.

Quality Improvement (QI) interviews:

After completion of the baseline visit and during the second 3-month period of the pre-implementation phase, the study team will complete an environmental scan comprised of QI interviews. We will recruit approximately 10 clinical (e.g., primary care providers, nurses, medical assistants) and 5 non-clinical staff per practice to complete the study measures on the implementation of ALTA and complete a baseline semi-structured interview. Additionally, a random sample of 30 clinical/nonclinical staff across the practices will be asked to complete a semi-structured interview. This sample size is based on our previous studies using similar data collection methods. Each interview will have a maximum duration of 15 minutes. We will use a CFIR-guided semi-structured interview protocol to help identify barriers and facilitators to the implementation of ALTA in Phase 2. In accordance with CFIR, we will develop an interview guide that will explore the following domains: 1) inner practice setting (e.g., leadership support, organizational capacity); 2) external environment (e.g., patient needs and resources, external resources and incentives), 3) MA characteristics (e.g., self-efficacy, knowledge and beliefs about patient-centered counseling), and 4) intervention characteristics (e.g., complexity). The interview will be completed in-person or virtually to accommodate to the current COVID-19 situation. The interview method (face-to-face face vs. virtual) will be determined at the discretion and preference of the participants, while following practices and NYU institutional regulations for COVID-19.

The Stakeholder Committee, in partnership with the study team, will use this data to develop a refined PF strategy tailored to the practice context and designed to overcome the challenges to implementation of ALTA into routine practice in the implementation phase. During this period, the study team will also hold a Kick-off Event at the practices that will include didactic and interactive sessions on topics such as: the ALTA model components; best practices for implementing team-based models of care; defining roles and responsibilities in interdisciplinary care teams; developing effective interdisciplinary and patient-centered communication skills; and a discussion of the implementation and evaluation process. All clinical and non-clinical staff as well as site leadership will be encouraged to attend the Kick-off Event.

As part of the implementation QI Interviews, patients who have been invited to participate in the program by their physicians and decline participation will be asked to complete questions regarding the reason for declining participation, as follows:

Patients who decline participation:

- Patients who refuse participation will be invited to complete an interview at checkout before leaving the clinic on the day when the program was offered to them, and they declined.
- The interview is voluntary and anonymous, and no private information (name, MRN, email, SS, dates, or other identifiable information will be collected).
- We are aiming to complete the interview with 60 patients across all participating sites.

Procedures to complete the interview with patients who decline participation:

- Study staff will be at the sites 2-3 times per week in the afternoon. When the research staff is at the sites, any patient who declines participation will be approached at check out and will be asked if they are interested in voluntarily answering a questionnaire about reasons for declining participation and ideas for improving the program. We will

continue to invite patients to voluntarily answer the anonymous interview until we reach 60 patients.

- Patients will be asked the following main questions:
 1. What are some ways that we could support you to manage your high blood pressure?
 2. In what ways might the ALTA program help you better manage your high blood pressure?
 3. What are your main reasons for declining participation in the ALTA program?
 4. Based on conversation today, is there anything we can do to change the ALTA program to make you more likely to sign up at your next clinic visit?
- Patients will be explained that a) participation is voluntary and won't affect their care received at the clinic, b) no identifiable information will be collected (name, MRN, email, SS, dates, or other identifiable information will be collected), and c) the answers will be used to improve the existing blood pressure program being offered at the clinic.
- Patients will be given hard copies of the questions and will be asked if staff can read those questions to them or if they prefer to answer the questions by themselves. A RedCap survey will be available to patients who opt to answer the questions by themselves. For patients who agree to answer the questions on site with assistance from staff, the patient will be taken to a private space at the clinic where the questions can be read to them.
- Patients will be asked if they need assistance administering the questions in their preferred language. The interpreter line will be used to assist patients who need interpretation, following current practices and policies at the sites.
- Study staff will assist clinical and non-clinical staff at the sites (e.g., RNs, CHWs, PCPs, NTV volunteering at the sites) complete the interviews with patients during clinical visits, 2-3 times per week in the afternoons. We will leverage existing resources at the sites for the interview and survey completion. For example, it is the standard of care coordination at the participating sites that CHWs conduct follow-up calls with patients to assist them with MyChart enrollment. Therefore CHWs, or NVTs already approved to work at the practices could be well suited to complete the interviews as part of their ongoing patient outreach.

Upon completing the interviews, study staff will meet with site leadership to review the information obtained and discuss changes needed to the program to increase patient participation. The analysis of the interviews will only be used to inform patient-driven modifications to the program to improve patient acceptance rates.

6.3.6 End of Study and Follow Up

Patient Consent at baseline: During this visit, trained RAs will use a standardized form to screen patients based on the study's inclusion and exclusion criteria. Verbal consent will be obtained prior to beginning the eligibility screening. Only patients that meet all eligibility criteria will then complete the consent procedures, during which a trained RAs will describe the study in easy-to-understand language. If the patient remains interested, the RA will obtain written informed consent in the patient's preferred language (English or Spanish). The patient will then complete a demographic questionnaire, validated surveys on patient trust, relationship commitment and anxiety, and have their medical chart reviewed by a trained RA. This visit should take 15 minutes.

Final study visit at 12-Months (post randomization): At 12 months, trained RAs will repeat the chart review procedures for consenting patients, in accordance with IRB and

HIPAA regulations. Patients will also complete the same measures on patient trust, relationship commitment and anxiety. In addition, we will conduct semi-structured interviews with a random sample of 30 patients with uncontrolled HTN about their experiences with ALTA over the past 12 months and its impact on the patient-provider relationship, as well as recommendations for improvements. This visit will take approximately 60 minutes.

Clinical/nonclinical staff 12 month visit survey: Clinical/nonclinical will be asked to complete measures regarding implementation leadership and climate, counseling self-efficacy, organizational capacity to change, individual attitudes toward evidence-based practices, the degree of buy-in among the change recipients, and provider trust. A trained RA will send an email with RedCap link containing consent to all clinical/nonclinical staff via a general email distribution list. After clicking on the link, potential participants will read the 'consent statement' which includes PI name, brief study purpose, details on voluntary participation, ability to stop at any time without explanation and further, that such action will in no way affect their relationship with the primary care practice, confidentiality (anonymous survey), risks/benefits, etc. The email will emphasize that participation is voluntary and refusal to participate will not affect employment or job performance evaluation. They will then be given the option of whether they choose to participate. If they choose to participate, they will proceed to the survey, otherwise, participants will terminate the survey.

Please note that the baseline and 12-month surveys are not linked. Staff will be consented at both baseline and final study visit.

Clinical/Nonclinical staff Consent Exit Interviews: In addition, a random sample of 30 clinical/nonclinical across all 10 practices will complete an exit interview where they will be queried about their experiences with ALTA and the PF intervention (if applicable) over the past 12 months, its impact on the patient-provider relationship, and recommendations for improvements. This visit should take 30 minutes.

Participation is voluntarily and those interested in participating will be encouraged to sign and date the consent form. The exit interviews will be completed in-person or virtually to accommodate to the current COVID-19 situation. The interview method (face-to-face face vs. virtual) will be determined at the discretion and preference of the participants, while following practices and NYU institutional regulations for COVID-19. Invitation to participate will be random. If staff expresses interest in participating, he/she will receive a RedCap link to the consent form. An RA will then proceed to arrange a meeting with staff to review the consent form and answer questions staff may have. Audio recording will be obtained and after the interview is recorded it will be transcribed and identifier removed to protect the subject.

6.3.7 Removal of Subjects

Subjects may withdraw voluntarily at any time for any reason.

Participants may also be withdrawn from the study for certain reasons. Some possible reasons for withdrawing a subject from the study would be worsening health or other conditions that might make it harmful for continued participation (as determined by their

primary care physician). In addition, participants may be withdrawn if they fail to comply with the study protocol, keep appointments or follow directions.

6.4.1 Statistical Design

The proposed project will evaluate, in a stepped-wedge cluster randomized controlled trial, the effect of the PF strategy on level of implementation fidelity (primary outcome) of ALTA, as well as on clinical outcomes (secondary outcomes), as compared to usual care at 12 months. Implementation fidelity will be assessed through a process evaluation using a mixed methods approach based on five core dimensions of implementation fidelity, as defined by Proctor's Implementation Outcomes Framework (described below). Clinical outcome measures include blood pressure (BP) control (defined as <140/90 mmHg) and medication adherence (assessed using the proportion of days covered [PDC] via pharmacy records). We will also examine change in systolic and diastolic blood pressure (SBP, DBP) as well as an alternate definition of BP control (<130/80 mmHg as per the new hypertension guidelines) in exploratory analyses.

6.4.2 Sample Size Considerations

Power calculations are based on the clinical outcome of BP control using our prior work implementing the ALTA model in a community-based clinic. In the former trial, we found a significant improvement in attainment of BP control at 6 months among patients randomized to the intervention group compared to the UC group (51% vs. 29%, $p=.03$). We expect a similar group difference of a 20% increase in BP control between the implementation and UC phases in the current study. Calculations of achieved power were estimated with a stepped-wedge design using Power Analysis and Sample Size (PASS) software program. The power calculations show that we can recruit 10 sites and 700 patients and have at least 80% power to detect a more conservative 15% difference in BP control between the UC and implementation phases for intraclass correlation coefficients (ICCs) ranging from 0.01 to 0.05. Using our original estimate of a 20% difference in BP control, we would have over 90% power to detect a difference between the UC and implementation phases with 10 sites and 700 patients.

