5.1 General Design

Using a stepped-wedge cluster randomized control trial design, this study will evaluate the effect of a tailored PF strategy on the implementation of Advancing Long-term Improvements in Hypertension Outcomes through a Team-based Care Approach (ALTA), our systems-level approach to improving medication adherence and BP control, among patients with uncontrolled HTN receiving care in 10 safety-net practices in New York.

Using a mixed-methods approach, this study will be conducted in two phases: (1) a pre-implementation phase where we will refine the PF strategy, based on the Consolidated Framework for Implementation Research (CFIR) to facilitate implementation of ALTA at the practices and (2) an implementation phase, guided by Proctor's Implementation Outcomes Framework (IOF). The primary aim of the implementation phase is to evaluate, in a stepped-wedge cluster randomized trial, the level of implementation fidelity (e.g., degree to which a program is delivered, as intended) of ALTA because of the tailored PF strategies. The secondary aims are to compare the effects of PF versus usual care (UC) on BP control and medication adherence in 10 safety-net primary care practices and patients with uncontrolled HTN who are non-adherent to their antihypertensive medications. We will also explore the potential moderating factors at the practice and individual levels (e.g., organizational capacity to change, evidence-based practice attitudes) that influence level of implementation fidelity of ALTA at the practices. We will also explore the impact of ALTA on the patient-provider relationship (i.e., relationship commitment, patient-provider trust, and patient anxiety in the interaction), and determine whether any changes to the relationship also affect patients' BP control and medication adherence.

As shown in Figure 1, each participating practice will start with the UC phase and are block-randomized into four waves, with two sites per wave. The UC phase will be followed by the pre-implementation phase of 6 months, during which facilitators will conduct a practice evaluation (e.g., workflow analysis, environmental scan) based on CFIR, refine the PF strategies that will be used in the implementation phase, and train staff in the ALTA model. Following this period, sites will implement ALTA with the assistance of the facilitator for 12 months, with a 3-month follow-up period for outcome assessment.

Figure 1. Stepped wedge design of ALTA implementation

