6.3.4 Recruitment, Enrollment and Retention

Practice clinical and non-clinical staff will be recruited through study team attendance at the monthly staff meetings, email communications that describe the project including the overarching goals and what is expected of participants, and in-person or virtual meetings with the practices.

We will recruit approximately 500 patients across the practices who meet the following eligibility criteria (described above). Several strategies will be used to maximize the number

of eligible patient participants recruited per practice as described below. Signed informed consent will be obtained from participants who meet the study eligibility criteria.

Since this is a clinic wide initiative, we are broadening our eligibility criteria to include patients of all race and ethnicities, and not be exclusive to Latinx patients (this is also reflected in the change to our project name). We will still recruit a random sample of 70 patients per clinic that receive care in the 10 safety-net practices to participate in the surveys to assess our tertiary outcomes. Of this sample, 30 will be randomly selected to participate in an exit interview. Patients will be randomly selected from a list of patients who receive care in the clinics and have been exposed to the ALTA project. The same recruitment strategies will be employed to recruit 300 patients who receive care in the clinics and met eligibility for ALTA but did not ultimately participate in the project. All patients will provide written informed consent prior to participating in the study.

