6.4.3.2 Secondary Objectives Analyses

The effect of PF on BP Control

Our main clinical outcome is the proportion of patients with adequate BP control (<140/90 mmHg) at 12 months in the implementation vs. UC phase. BP control will be treated as a dichotomous outcome variable in this analysis; any patients with missing follow-up BP data will be assumed to have inadequate BP control. To examine the difference in BP control rates between the implementation and UC phases, we will utilize a generalized linear mixed model (GLMM) to assess the PF effect. A Poisson regression model will be used to predict BP control specifying a fixed effect for time, a fixed effect for treatment and a time by treatment interaction. Random effects will be specified for person and practice to account for the clustered nature of the dataset (observations within person and people within practices). As a sensitivity analysis, we will also assess an alternate definition of BP control (< 130/80 mmHg) indicated by the new hypertension guidelines. In exploratory analyses, will examine the intervention effect on BP reduction at 12 months, treated as a continuous variable. An additional sensitivity analysis will be conducted using GLMM to evaluate the effect of PF on BP reduction. We will test the treatment X time interactions in a random effects linear regression model to determine the time-specific differences BP reduction attributable to PF at the end of the implementation phase.

Randomization of the stepped-wedge design should obviate the need for adjustment, but in the case of imbalanced in baseline covariates; these will be included as necessary in adjusted analyses. All tests will be two-sided with $\alpha=0.05$ for comparison between the implementation and UC phases. Maximum likelihood estimation of mixed-effects models will be used to account for missing data; in the context of a mixed-effects model, this is equivalent to an assumption of data that are missing at random (MAR); we will conduct sensitivity analyses assessing this assumption. We will also compare participants with and without missing values with respect to baseline and practice characteristics. If differential patterns emerge, we will consider the use of multiple imputation and/or inverse probability weighting to adjust for missing data. Analyses will be conducted using Stata, SAS, and R.

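### The stated power for BP control rests on 10 sites and 700 patients, but other sections imply 8 sites or about 500 patients, and the calculation omits the inputs needed to verify it

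*Combined protocol and SAP*

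**What the plan says.** The only power statement is in section 6.4.2 and concerns BP control, a secondary outcome. It reads: "The power calculations show that we can recruit 10 sites and 700 patients and have at least 80% power to detect a more conservative" effect, which is then given as 15 percentage points, for ICCs between 0.01 and 0.05. For 20 points, "we would have over 90% power to detect a difference between the UC and implementation phases with 10 sites and 700 patients". The section cites a stepped-wedge calculation in PASS and quotes the prior trial's rates, 51% against 29%.

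Three other places bear on those figures:

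- **Sites.** Section 5.1 says practices are "block-randomized into four waves, with two sites per wave". The same section refers to 10 practices, section 5.1.2 gives 10, and Figure 1 has five cohorts.
- **Patients.** Section 6.3.4 says: "We will recruit approximately 500 patients across the practices who meet the following eligibility criteria". Its next paragraph gives 70 per clinic in 10 practices. The Synopsis and section 5.3.1 also give 700.
- **Missing data.** Section 6.4.3.2 says "any patients with missing follow-up BP data will be assumed to have inadequate BP control". Section 6.4.2 makes no allowance for this.

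**The concern.** Four waves of two sites is 4 x 2 = 8, and section 5.1 is the only text that gives the randomisation structure. Read literally, it leaves two of the ten practices without a randomised step. The patient number differs by 200 within one section. Both are inputs to the stated power.

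Separately, section 6.4.2 does not give the UC rate used for the 15-point case, the number of steps, the patients per site and period, whether sampling is cross-sectional or cohort, or any attrition. It does not mention the two quarters of pre-implementation that Figure 1 places between UC and intervention. A reader cannot tell which trial the 80% and 90% describe. A null BP result could then be read as coming from an adequately powered comparison when that has not been shown.

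**Working it through.** **Inputs from the plan.** Differences of 15 and 20 points, and ICC 0.01 to 0.05 (6.4.2). Two-sided alpha 0.05 (6.4.3.2): "All tests will be two-sided with $\alpha=0.05$ for comparison between the implementation and UC phases". Sites 10 or 8; patients 700, 500, or 8 x 70 = 560.

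**Inputs assumed.** UC rate 29% (the prior trial's rate; 6.4.2 does not say it was used), one outcome per patient, outcomes spread evenly over a complete wedge with two sites per step.

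**Formula.** Hussey-Hughes, with fixed period effects and a random site intercept. Let I = sites, T = periods, m = patients per site-period, v = pbar(1 - pbar), s2 = (1 - ICC)v/m and t2 = ICC x v. Let U be the number of treated site-periods, W the sum over periods of (treated sites)^2, and V the sum over sites of (treated periods)^2.

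Var = I s2 (s2 + T t2) / [(IU - W) s2 + (U^2 + ITU - TW - IV) t2]; power = Phi(difference/SE - 1.96).

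**The plan's own case: 10 sites, 700 patients, 15 points.** I = 10, T = 6, m = 700/60 = 11.67, U = 30, W = 220, V = 110. So IU - W = 80 and the other bracket is 900 + 1800 - 1320 - 1100 = 280. pbar = (0.29 + 0.44)/2 = 0.365, so v = 0.2318.

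- ICC 0.01: s2 = 0.01967, t2 = 0.00232, SE = 0.0545, power = Phi(2.75 - 1.96) = 78.6%.
- ICC 0.05: s2 = 0.01887, t2 = 0.01159, SE = 0.0592, power = Phi(2.53 - 1.96) = 71.6%.

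So 80% is nearly met at ICC 0.01 and missed at 0.05. The Woertman design effect agrees (78.9% / 71.9%).

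**All readings, same model, ICC 0.01 / 0.05:**

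| Sites / patients | 15 points | 20 points |
|---|---|---|
| 10 / 700 | 78.6% / 71.6% | 95.2% / 91.5% |
| 10 / 500 | 66.0% / 58.7% | 87.7% / 81.9% |
| 8 / 560 | 66.8% / 60.0% | 88.3% / 83.0% |
| 8 / 500 | 62.4% / 55.7% | 85.0% / 79.1% |

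The 20-point claim of over 90% reproduces at 10 / 700 and fails in the other rows.

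**Sensitivity to unstated inputs (10 / 700, 15 points).**

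- UC rate 20%: 84.3% / 77.9%.
- UC rate 15%: 88.7% / 83.1%.
- UC-rate variance at 29%: 83.1% / 76.6%.
- Two outcomes per patient, treated as independent on a complete wedge: 96.1% / 93.5%.

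**Missing counted as uncontrolled.** Assume 20% of follow-up BP is missing; the plan gives no figure. The rates become 0.8 x 29% = 23.2% and 0.8 x 44% = 35.2%, a 12-point difference with pbar = 0.292. At 10 / 700 the SE is 0.0515 / 0.0559 and power is about 64% / 57%.

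**Figure 1 layout.** The extracted table has merged cells. My reading is a one-quarter stagger, UC ending in quarter 2 for cohort 1 and quarter 6 for cohort 5, two quarters of pre-implementation, then four of intervention. Outcomes are spread over UC and intervention quarters only. UC starting in quarter 1 gives 80 site-quarters; starting in quarter 2 gives 70.

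| Outcomes | UC from quarter 1 | UC from quarter 2 |
|---|---|---|
| 700 | 30.1% / 27.9% | 33.1% / 29.9% |
| 1,400 | 50.7% / 47.7% | 54.9% / 50.3% |

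The main BP outcome is at 12 months. Cohort 1's intervention runs over quarters 5 to 8 and its outcome evaluation is in quarter 9, while the last UC quarter in any cohort is 6. No 12-month outcome therefore shares a calendar quarter with a UC period. With categorical calendar-quarter effects and treated outcomes only at 12 months, the design matrix is singular and the phase effect cannot be separated from time.

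**The case against.** Most of the protocol supports 10 sites and 700 patients: the Synopsis, sections 5.1.2 and 5.3.1, the five cohorts, and two facilitators with five practices each. The four waves and the 500 may well be leftover text. That stands. A reader might infer that two practices were in fact left unrandomised, but the documents contain no randomisation list and do not show this.

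A reader might also infer that the PASS result is an arithmetic error. The documents do not support that either. The 10 / 700 shortfall depends on inputs that I supplied. Eligible patients have average BP of at least 140/90 and adherence below 80%, so a UC rate below 29% is plausible, and at 15% the claim is met across the ICC range. Nor should the scenarios be merged into one range of about 59% to 79%. Its ends would be 10 / 500 at ICC 0.05 and 10 / 700 at ICC 0.01, with no 8-site case in it.

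The strongest point is that BP is measured at baseline and at 12 months and the model has a person random effect. Counting both outcomes keeps even 8 sites and 500 patients above 80% (87.0% / 82.3%). This does not rescue the claim. It ignores within-person correlation and needs UC and treated outcomes to overlap in calendar time, which Figure 1 does not provide for 12-month outcomes. Baseline is also not an ordinary UC outcome, because eligibility makes control at baseline rare. The overlap objection applies equally to the one-outcome table, which is therefore a benchmark on a complete wedge and not an estimate of this trial's power.

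**Conclusion.** The point holds in a limited form, and its severity is moderate. The site and patient contradictions are in the text and need no model. The claims of at least 80% and over 90% cover only 10 sites and 700 patients and cannot be verified from what is stated.

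Under the stated assumptions, moving from 10 / 700 to the other documented counts costs about 12 to 16 points of power for the 15-point difference and takes the 20-point figure below 90%. The shortfall at 10 / 700 itself is conditional: it disappears at a 15% UC rate. The largest loss comes from the Figure 1 layout, at about 28-33% with 700 outcomes and 48-55% with 1,400, subject to my reading of a broken table and to how calendar time enters the model, which the plan does not specify. BP control is secondary; the primary outcome, implementation fidelity, has no power statement and is not affected by this calculation.

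**What to change.** 1. Correct section 5.1 to five waves of two sites, to match Figure 1 and the 10 practices. If 8 sites is intended, restate every dependent figure for 8.
2. Use one patient number in sections 5.3.1, 6.3.4, 6.4.2 and the Synopsis.
3. Re-run power on the Figure 1 pattern, including the pre-implementation gap. State the UC rate, steps, patients per site-period, outcomes per patient, cross-sectional or cohort sampling, ICC, how calendar time is modelled, and the dilution from counting missing BP as uncontrolled.
4. Replace the 80% and 90% statements with the figures obtained, by scenario.

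The cost is wording changes and one recalculation, probably with a less favourable stated power for a secondary outcome. No extra enrolment is proposed.
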